2.1. Primary Objectives

The primary objectives of this study were as follows:

- To assess the safety and tolerability of AZD4041 following oral administration of single ascending doses
- To characterize the PK of AZD4041 following oral administration of single ascending doses of AZD4041

2.2. Secondary Objective

The secondary objective of this study was to characterize the pharmacodynamic (PD) relationship between drug exposure and QT interval.

3. Investigational Plan

3.1. Overall Study Design and Plan

This is a Phase I, first-in-human, single-center, randomized, double-blind, placebo-controlled, single ascending dose, sequential group study in healthy male and female subjects of non-childbearing potential (Cohorts 1, 2, and 3), or healthy vasectomized male and female subjects of non-childbearing potential (Cohorts 4, 5, and 6), aged 18 to 65 years.

The study plans to enroll 48 healthy subjects across 6 cohorts as shown in Table 3-1.

Table 3-1: Dose-Level Cohorts

Cohort	Dose Level of AZD4041
[REDACTED]	[REDACTED]

Eight subjects will participate in each cohort. Within each cohort, 6 subjects will be randomized to receive AZD4041 and 2 subjects will be randomized to receive placebo. Subjects that drop out before dosing will be replaced. Dosing for each ascending dose cohort will proceed with 2 subjects in a sentinel cohort, such that 1 subject will be randomized to receive placebo and 1 subject will be randomized to receive AZD4041 in a blinded fashion.

The safety data from the sentinel subjects up to 24 hours post-dose will be reviewed by the principal investigator (PI), clinical research organization (CRO) medical monitor, and AstraZeneca study physician before the remaining subjects in the cohort are dosed. The remaining 6 subjects for each cohort will be dosed at least 24 hours after the sentinel cohort.

The study comprises a screening period of up to 28 days (4 weeks), a 4-day in-patient period for Cohorts 1 to 3 and a 6-day in-patient period for Cohorts 4 to 6 during which a single oral dose of AZD4041 or placebo will be administered, and an out-patient follow-up period. The overall study duration (screening, treatment, and follow-up periods) will therefore be approximately 6 weeks. The general study design is summarized in Figure 3-1.

Figure 3-1: Study design (Cohorts 1 to 3)

[figure not shown]
[figure not shown]

Figure 3-2: Study design (Cohorts 4 to 6)

The end of study is defined as the last expected visit/contact of the last subject undergoing study treatment. A subject is considered to have completed the study when the subject has completed his/her last scheduled visit or last scheduled procedure, presented in Appendix 14.1 Schedule of Activities (SoA).

3.2. Study Endpoints

3.2.1. Primary Endpoints

Safety endpoints include the following:

- The frequency and severity of adverse events (AEs)
- Clinical laboratory test results (hematology, biochemistry, and urinalysis)
- Vital sign measurements (systolic and diastolic blood pressure, pulse rate, respiratory rate, and body temperature)
- 12-Lead ECG (paper ECG and digital ECG) and telemetry results
- Testosterone, luteinizing hormone (LH), follicle stimulating hormone (FSH), and inhibin B (male subjects in Cohorts 4, 5, and 6 only)

PK endpoints include the following:

- Maximum (peak) plasma drug concentration (C_{max})
- Time to reach maximum (peak) plasma concentration following drug administration (T_{max})
- Area under the plasma concentration versus time curve from time zero to the last quantifiable concentration in plasma (AUC_{0-t})
- Extrapolation of the area under the curve from time 0 to infinity (AUC_{0-inf})
- Terminal half-life ($t_{1/2\lambda_z}$)
- Apparent total clearance of the drug from plasma after oral administration (CL/F)
- Apparent volume of distribution at steady state after oral administration (V_{ss}/F)

3.2.2. Secondary Endpoints

An exposure-response (E-R) analysis may be conducted with data from this study alone or in combination with other studies as appropriate, with a pre-specified workflow described in a separate technical document, for the QT interval corrected for heart rate using Fridericia's formula (QTcF) parameter, as part of the cardiac safety evaluation and with the intention to obtain a Thorough QT (TQT) study substitute. The results of the E-R analysis may not be included in the main study report.

4. General Statistical Considerations

All statistical analyses will be performed using Statistical Analysis System (SAS[®]) software (SAS Institute Inc., Cary, North Carolina) Version 9.4 or higher.

For categorical variables, number and percentage of subjects will be presented. Percentage will be rounded to 1 decimal place and will be suppressed when the corresponding number of subjects is zero.

Continuous variables will be summarized using descriptive statistics and will include number of subjects, mean, median, standard deviation (SD), minimum, and maximum, unless otherwise specified. Geometric mean and coefficient of variation (CV) will also be presented for PK parameters. Minimum and maximum will be presented to the same precision as the original data, mean, median, and geometric mean will be presented to 1 more decimal place than the original data, and SD and CV will be presented to 2 more decimal places than the original data.

Study day will be calculated as follows:

- If assessment date is on or after the date of study drug administration, then Study Day = Assessment Date – Dose Date + 1
- Otherwise, Study Day = Assessment Date – Dose Date

All data collected on the electronic case report form (eCRF) will be presented in data listings by cohorts and subject where applicable.

Baseline will be defined as the last non-missing assessment prior to the study drug administration, including assessments from unscheduled visits. Unscheduled visits will not be included in summaries except for determining baseline. If there are repeated assessments at a post-dose time point, the first non-missing assessment will be included in the summary tables.

For blood pressures summaries, the average of triplicate measurements obtained at predose on Day 1 will be used as the baseline, and the average of triplicate measurements at post dose timepoints will be used.

Missing or partial date values will not be imputed unless otherwise stated.

Subjects who received placebo will be pooled across cohorts for summary purpose.

4.1. Randomization, Stratification, and Blinding

Approximately 48 subjects will be randomized in this study (8 subjects in each cohort). Within each cohort, 2 sentinel subjects will be randomized in 1:1 ratio to receive AZD4041 or placebo, and the remaining 6 subjects will be randomized to receive AZD4041 or placebo in 5:1 ratio, following review of sentinel safety data up to 24 hours post-dose. Subjects that drop out before dosing will be replaced.

This is a double-blind study. Neither the subjects nor the investigator will be aware of the treatment assignment. Blinding will be maintained throughout the study by use of active and placebo dosage forms of similar appearance. Access to the randomization code will be strictly controlled according to the standard operating procedures of PPD.

Blind breaking envelopes will be prepared. A subject or subjects may be unblinded in the event of a dose-limiting toxicity, serious adverse event (SAE), or other event, or if there is a medical emergency where the identity of the drug must be known to properly treat a subject. Data will be reviewed blinded by the safety review committee (SRC), but if the PI or the SRC consider it necessary due to a safety concern, data from individual subjects or the entire cohort may be unblinded to enable decision-making. If a subject becomes seriously ill or pregnant during the study, the blind will be broken only if knowledge of the administered study drug will affect that subject's treatment options. In the event of a medical emergency requiring identification of the study drug administered to an individual subject, the investigator will make every attempt to contact the medical monitor to explain the need for opening the code within 24 hours of opening

the code. The investigator will be responsible for documenting the time, date, reason for the code break, and the names of the personnel involved.

4.2. Sample Size

Due to the exploratory nature of the study, sample size is not based on formal statistical considerations but is based primarily on a desire to obtain sufficient safety and tolerability information while exposing as few subjects as possible to the investigational treatment.

4.3. Analysis Population

The safety analysis set will include all subjects who receive AZD4041 or placebo and have any post-dose safety data.

The PK analysis set will include all subjects who receive AZD4041 and have any PK data.

5. Subject Disposition

5.1. Disposition

Number and percentage of subjects who were screen failures, who were randomized, who completed the study, and who did not complete the study, along with the reason for not completing the study, and the number and percentage of subjects included in each analysis population, will be summarized by treatment and overall for all screened subjects.

Subject disposition will be presented in a data listing. Subjects excluded from the analysis populations and the reasons for exclusion will be presented in a data listing.

5.2. Protocol Deviations

Protocol deviations will be summarized by treatment and overall for the safety analysis set and presented in a data listing.

6. Demographics and Baseline Characteristics

6.1. Demographics

The demographics information, including age, sex, ethnicity, race, screening weight, screening height, and screening body mass index (BMI) will be summarized by treatment and overall for the safety analysis set.

Subject demographics and baseline characteristics will be presented in a data listing.

6.2. Medical History

Medical history will be coded by system organ class (SOC) and preferred term using the Medical Dictionary for Regulatory Activities (MedDRA), version to be delineated in the clinical study report (CSR).

Medical history data will be presented in a data listing.

7. Treatments and Medications

7.1. Prior and Concomitant Medications

A prior medication is defined as any medication that ends prior to the study drug administration. A concomitant medication is defined as any medication that starts on or after the time of study drug administration. Medications that started prior to the study drug administration but ends after the study drug administration or are ongoing will be considered both prior and concomitant.

All prior and concomitant medications will be coded using the World Health Organization Drug Dictionary, version to be delineated in the CSR, and will be presented in a data listing.

7.2. Medical or Surgical Treatment Procedures

Medical or surgical treatment procedures which occur during the study will be presented in a data listing.

7.3. Study Treatments

Study drug administration data will be presented in data listings. Overdose information will be presented in a data listing as well.

8. Safety Analysis

All safety analyses will be based on the safety analysis set unless otherwise specified.

8.1. Adverse Events

An AE is the development of any untoward medical occurrence in a subject or clinical study subject administered a medicinal product and which does not necessarily have a causal relationship with this treatment. An AE can therefore be any unfavourable and unintended sign (eg, an abnormal laboratory finding), symptom (eg, nausea, chest pain), or disease temporally associated with the use of a medicinal product, whether or not considered related to the medicinal product.

A treatment-emergent AE (TEAE) is defined as any event not present before exposure to study drug or any event already present that worsens in intensity or frequency after exposure.

All AEs will be coded by SOC and preferred term using MedDRA, version to be delineated in the CSR.

8.1.1. Incidence of Adverse Events

Number and percentage of subjects with AEs will be presented in summary tables. A subject with 2 or more AEs within the same SOC and preferred term will be counted once in summarization level.

An overview of AEs, including number of subjects with at least one AE, with at least one TEAE, with at least one treatment-related TEAE, with at least one moderate TEAE, with at least one treatment-related moderate TEAE, with at least one severe TEAE, with at least one treatment-related severe TEAE, with at least one SAE, with at least one treatment-related SAE, with at least one TEAE leading to early discontinuation, and death will be presented by treatment and overall.

Summary tables will also be provided for all TEAEs by SOC, preferred term, treatment and overall.

All AEs will be presented in a data listing.

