1 PROTOCOL SUMMARY

1.1 Schedule of Activities (SoA)

Table 1 Schedule of Activities - Cohorts 1 to 3

	Screening Day -28 to Day -2	Day -1	Day 1	Day 2	Day 3	Follow-up Visit ^a (14 days post-dose)
Informed consent	X					
Inclusion/exclusion criteria	X	X	X			
Demographic data	X					
Medical history	X					
Urinary drug screen	X	X				
Alcohol screen	X	X				
Testing for HIV, hepatitis B and C	X					
Pregnancy testing ^b	X	X				
FSH testing in women	X					
Randomization			X			
Admission to CRU		X				
Discharge from CRU					X	
Height, body weight, and BMI ^c	X	X			X	X
Study drug administration			X			
Adverse event recording	X	X	X	X	X	X
Blood pressure, temperature, respiratory rate, and pulse rate	X	X	X ^d	X	X	X
12-lead paper safety ECG	X	X	X ^e	X ^e	X ^e	
12-lead digital ECG			X ^e	X ^e	X ^e	
Telemetry ^f		X	X			
Clinical laboratory evaluations ^g	X	X		X		X
Physical examination	X	X			X	X
Blood sampling for PK ^h			X	X	X	

^a Tests will be performed at follow-up and also in cases of discontinuation.

^b Serum pregnancy test will be performed at screening and check-in.

^c Height will be measured at screening only.

^d Blood pressure, temperature, respiratory rate, and pulse rate will be measured at pre-dose, then at 1, 2, 3, 4, 6, 8, 12, 24, and 48 hours post-dose.

^e Paper and digital ECGs will be collected at the same time points as PK sampling. Recording of ECGs will precede PK sampling and check of vital signs at each time point.

- f Telemetry for 4 to 6 hours on Day -1 to establish a baseline. Pre-dose to 24 hours post-dose.
- g Clinical laboratory assessments must be repeated if first collected more than 2 weeks before dosing.
- h Blood samples will be collected at pre-dose, then at 0.25, 0.5, 1, 1.5, 2, 3, 4, 6, 8, 12, 24, 36, and 48 hours.

BMI body mass index; CRU Clinical Research Unit; ECG electrocardiogram; FSH follicle stimulating hormone; HIV human immunodeficiency virus; PK pharmacokinetic(s)

Table 2 Schedule of Activities - Cohorts 4 to 6

	Screening Day -28 to Day -2	Day -2	Day -1	Day 1	Day 2	Day 3	Day 4	Follow-up Visit ^a (14±2 days post-dose)
Informed consent	X							
Inclusion/exclusion criteria	X		X	X				
Demographic data	X							
Medical history	X							
Urinary drug screen	X		X					
Alcohol screen	X		X					
Testing for HIV, hepatitis B and C	X							
Pregnancy testing ^b	X		X					
FSH testing in women	X							
Randomization				X				
Admission to CRU		X						
Discharge from CRU							X	
Height, body weight, and BMI ^c	X		X				X	X

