For cohorts 1, 2 and 3 the predicted exposure was planned not exceed a limit that is approximately 10-fold below the NOAEL exposures in males in the Dog 28-day study (Table 4). Subsequent cohorts in females of non-childbearing potential and vasectomised males have revised exposure limits that is proposed not to exceed the intermediate dose NOAEL exposures in the female dog at [REDACTED]. Utilizing geometric mean data, observed exposures at [REDACTED] provide a [REDACTED] margin to free C_{max} and an [REDACTED] margin to free AUC_{0-inf} when compared to the female dog NOAEL derived from the 28 Day GLP toxicology study (Table 5). For the partial Cohort 5 data at [REDACTED] geometric mean data indicates a [REDACTED] margin to free C_{max} and an [REDACTED] margin to free AUC_{0-inf} when the same comparison is made to the female dog NOAEL exposures.

Table 4 Observed exposures and margins to male dog NOAEL

Clinical dose (mg)	Human free C_{max} (ng/mL)	Human free $C_{max}/Dose$	C_{max} margin to male dog NOAEL	Human free AUC_{0-inf} (ng·h/mL)	Human free $AUC_{0-inf}/Dose$	AUC_{0-inf} margin to male dog NOAEL
[REDACTED]	[REDACTED]	[REDACTED]	[REDACTED]	[REDACTED]	[REDACTED]	[REDACTED]
[REDACTED]	[REDACTED]	[REDACTED]	[REDACTED]	[REDACTED]	[REDACTED]	[REDACTED]
[REDACTED]	[REDACTED]	[REDACTED]	[REDACTED]	[REDACTED]	[REDACTED]	[REDACTED]

AUC_{0-inf} Extrapolation of the area under the curve from time 0 to infinity; C_{max} Maximum (peak) plasma drug concentration; NOAEL No-observed-adverse-effect level

n/a = not applicable since male dog NOAEL was not utilized as exposure limit beyond Cohort 3

Note: Exposures are provided as geometric means (n=6).

Pharmacokinetic data within cohorts indicated that there was some variability in systemic exposure between individuals. As an example in Cohort 3, the coefficient of variation for C_{max} geometric mean was 24.7% and the coefficient of variation for AUC_{0-inf} geometric mean was 43.7%. For 3 subjects within Cohort 3, extrapolation of AUC_{0-inf} following noncompartmental analysis was >20%, indicating some uncertainty in the calculation of this parameter. However, with an extended sampling period and extrapolation of AUC_{0-inf} following noncompartmental analysis of <20% in all subjects, variability in systemic exposure was still evident in Cohort 4, as exemplified by a coefficient of variation for C_{max} geometric mean of 21.2% and a coefficient of variation for AUC_{0-inf} geometric mean of 52.4%.

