8.3.4 Adverse event data collection

The following variables will be collected for each AE:

- AE (verbatim)
- The date and time when the AE started and stopped
- Intensity of the AE
- Whether the AE is serious or not
- Investigator causality rating against the IP (yes or no)
- Action taken with regard to IP
- Whether the AE caused the subject's withdrawal from study (yes or no)
- Outcome of the AE

In addition, the following variables will be collected for SAEs:

- Date AE met criteria for SAE
- Date Investigator became aware of SAE
- AE is serious due to
- Date of hospitalization
- Date of discharge
- Probable cause of death

- Date of death
- Autopsy performed
- Causality assessment in relation to study procedure(s)
- Causality assessment to other medication
- Description of the SAE

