9.4.2.1 Safety and tolerability

Adverse events will be listed and summarized by Medical Dictionary for Regulatory Activities system organ class and preferred term, and by treatment regimen. The presentation period of AEs will be the time from first dose to follow-up.

Vital signs, body temperature, body weight and BMI, clinical laboratory measures, and dECG interval data will be summarized using descriptive statistics by treatment regimen and CSP time (eg, visit number, date, and time).

Individual data for vital signs, body weight and BMI, clinical laboratory measures, dECG intervals, overall pECG assessments (made by the Investigator), and physical examination results will be flagged and listed for any potentially clinically important (PCI) values for each subject according to predetermined PCI criteria.

Project-specific reference limits will be used in the statistical analysis. When project-specific reference limits are not available, the reference limits of the local laboratory will be used.

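### TEAE tables set Cohorts 1-3 (in-house AE questioning to 48 h) beside Cohorts 4-6 (to 72 h) and one placebo group drawn from both, with no same-schedule placebo column; the likely distortion is small and cheap to expose

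*SAP*

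**What the plan says.** SAP 3.1 gives "a 4-day in-patient period for Cohorts 1 to 3 and a 6-day in-patient period for Cohorts 4 to 6". In Protocol Tables 1 and 2, the row "Adverse event recording" is marked on Days 1, 2, 3 and follow-up for Cohorts 1-3, and on Days 1, 2, 3, 4 and follow-up for Cohorts 4-6. Discharge is on Day 3 and Day 4 respectively. Neither schedule has a visit or call between discharge and follow-up.

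On reporting, Protocol 9.4.2.1 states: "The presentation period of AEs will be the time from first dose to follow-up". SAP 8.1.1 adds: "Summary tables will also be provided for all TEAEs by SOC, preferred term, treatment and overall". The tables by relationship and by severity (SAP 8.1.2 and 8.1.3) have the same layout. SAP Section 4 says: "Subjects who received placebo will be pooled across cohorts for summary purpose". The allocation in SAP 3.1 is: "Within each cohort, 6 subjects will be randomized to receive AZD4041 and 2 subjects will be randomized to receive placebo".

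The SAP has no TEAE table limited to a common onset window, no split by schedule, and no remark on the difference. The protocol does collect "The date and time when the AE started and stopped" for each AE (8.3.4).

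**The concern.** AEs are a primary safety endpoint, and Protocol 2.2.2 relies on AE reporting to detect effects on sleep and wakefulness. AEs come from spontaneous report, observation and an open question from site staff (Protocol 8.3.6). For onsets at 48-72 h, Cohorts 4-6 are observed and asked at the time, whereas Cohorts 1-3 must recall the event at a visit 11 to 12 days later.

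Schedule is fully confounded with cohort, and with dose level if doses rise with cohort (the doses are redacted). Pooled placebo does not remove the imbalance, because half of it followed each schedule. Drug-related events after 48 h are plausible: Protocol 2.3 reports that 3 Cohort 3 subjects had more than 20% of AUC extrapolated, and that longer sampling brought this below 20% in every Cohort 4 subject. Some excess of mild, late events in Cohorts 4-6 could therefore reflect closer questioning rather than dose.

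**Working it through.** **1. The plan's own figures.** Days in the unit are {-1, 1, 2, 3} = 4 and {-2, -1, 1, 2, 3, 4} = 6, as stated. Total N = 6 × (6 + 2) = 48, as stated. Placebo is 6 × 2 = 12: 3 × 2 = 6 from each schedule.

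**2. Follow-up intensity.** In-house post-dose time is 48 h against 72 h (ratio 1.5); pooled placebo averages (6 × 48 + 6 × 72)/12 = 60 h. The gap to a visit on day 14 is 12 days in Cohorts 1-3 and 11 days in Cohorts 4-6 (9 to 13 with the ±2 days in Table 2). The discharge days come from Protocol Tables 1 and 2. In the available text of SAP Appendix 14.1 the Cohorts 1-3 discharge mark falls under follow-up, which may be a table-conversion fault.

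**3. Effect on any TEAE over the full period.** The documents give no AE rate or recall rate, so both are assumed: constant hazard L per day, full capture in-house, and a share r of out-patient events recalled at follow-up.

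- Cohorts 1-3: P = 1 − exp(−L(2 + 12r))
- Cohorts 4-6: P = 1 − exp(−L(3 + 11r))

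Example, L = 0.1 and r = 0.5: 1 − exp(−0.80) = 55.1% against 1 − exp(−0.85) = 57.3%, a gap of 2.2 points, or 6 × 0.022 = 0.13 subject per group of 6.

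| L per day | Cohorts 1-3, r = 0.5 | Cohorts 4-6, r = 0.5 | Gap in points, r = 0.5 | Gap, r = 0.25 | Gap, r = 0 |
|---|---|---|---|---|---|
| 0.02 | 14.8% | 15.6% | 0.8 | 1.3 | 1.9 |
| 0.05 | 33.0% | 34.6% | 1.7 | 2.9 | 4.4 |
| 0.10 | 55.1% | 57.3% | 2.2 | 4.4 | 7.8 |
| 0.20 | 79.8% | 81.7% | 1.9 | 5.1 | 12.2 |

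Gaps are taken from unrounded values. Per group of 6 they are 0.05-0.13 subject at r = 0.5, 0.08-0.31 at r = 0.25 and 0.11-0.73 at r = 0. At r = 1 the gap is zero. One subject in 6 is 16.7 points.

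**4. Against pooled placebo.** Placebo is the average of the two schedules, so each block departs from it by half the gap: at most 12.2/2 = 6.1 points, up for Cohorts 4-6 and down for Cohorts 1-3.

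**5. Why the window matters.** Take a 30% AE rate in 72 h, so L = −ln(0.7)/3 = 0.119 per day, with 50% recall. Counting 0-72 h only, the short-stay arms record 1 − exp(−0.357 × 5/6) = 25.7%, which is 4.3 points low. Over the full period that the SAP tabulates, the figures are 61.4% and 63.6%, a gap of 2.2 points. The gap shrinks because a subject with any other recorded event up to day 14 is counted anyway.

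**6. Clustering.** If events are not uniform in time, the gap is at most q(1 − r), where q is the probability that a subject's first AE has onset at 48-72 h. With q = 20% and r = 0.5 this is 10 points, or 0.6 subject per 6. Nothing in the documents shows such clustering.

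**7. A 48 h onset window.** Both blocks then have 2 in-house days, and the discharge-time gap is zero (at L = 0.1, 1 − exp(−0.2) = 18.1% in each).

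**The case against.** The strongest reply is that nothing goes uncollected. AEs are gathered from dosing to follow-up in every cohort, and the question covers the time since the subject was last asked. The tables are descriptive, and the SAP plans no test on AEs. Dose escalation rests on the Safety Review Committee's cohort-by-cohort review, which includes onset and duration (Protocol 8.4.6). AEs are also listed in full, so a reader can find onset times. All of this stands, and it keeps the point small. It does not remove it: the summary tables put dose levels beside placebo, and readers will compare the columns without reconstructing the schedules.

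A second reply is that a 48 h window is not captured identically either. Post-dose telemetry runs to 24 h in Cohorts 1-4 and the first 5 subjects of Cohort 5, and to 48 h afterwards (Protocol Tables 1 and 2). Men in Cohorts 4-6 also have repeated hormone sampling. A 48 h table would leave out later-onset events in a first-in-human study. This also stands, and is why that table should be supplementary and not the designated dose comparison.

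**Conclusion.** The plan compares blocks with unequal AE questioning at 48-72 h and offers no like-for-like view. The expected effect on the full-period tables is about 1-2 points at 50% recall, well under one subject per group of 6. It reaches about 12 points only if nothing is recalled and the hazard is at the top of the assumed range. Against pooled placebo, halve these. The direction favours more recorded events in Cohorts 4-6.

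A reader might infer that AE ascertainment rises from cohort to cohort and can by itself imitate a dose effect. The documents do not support that. There is one step, between Cohorts 3 and 4, so this mechanism cannot produce a trend within Cohorts 1-3 or within Cohorts 4-6, and its size under the assumed constant hazards is below one subject per group. Shortfalls worked out over 0-72 h alone also overstate the effect on the tables the SAP will produce (step 5).

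The sizes rest on assumed hazards and recall. The schedule facts and the pooling do not. This is a cheap improvement, not a threat to the trial's conclusions.

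**What to change.** In SAP 8.1.1:

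- Keep the full-period TEAE table as the main table.
- Beside the pooled placebo column, show placebo for Cohorts 1-3 and for Cohorts 4-6, so that each dose can be read against placebo on its own schedule.
- Add a supplementary TEAE table by SOC, preferred term and treatment, limited to onset within 48 h of dosing.
- State the schedule difference as a limitation, noting that post-dose telemetry also lengthens from 24 h to 48 h within Cohort 5.

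The cost is one table, two columns and a sentence, from onset dates and times already collected. The downsides are that the split placebo columns hold only 6 subjects each, and that the 48 h table omits later onsets, which stay in the full table.

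Separately, Protocol 2.2.2 describes confinement from the day before dosing to 72 hours after it, without distinguishing cohorts. Table 1 discharges Cohorts 1-3 on Day 3, and Table 2 admits Cohorts 4-6 on Day -2. These passages must be reconciled.
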